6.0 Study Objectives

6.1 Primary Objective

The primary objective of this study is to provide, under well-controlled conditions, continued access to LCIG treatment to subjects who have already participated in an open-label efficacy and safety trial with the same treatment (Study S187.3.003 or S187.3.004), and in whom the need for such continuation is indicated, as confirmed by periodic evaluation, until the product is commercially available.

6.2 Secondary Objectives

To assess the long-term safety and tolerability of the LCIG therapeutic system, and to assess the maintenance of efficacy using data collected from US subjects.

Safety and tolerability will be assessed by the following:

- Physical examination, including weight
- Neurological examination
- Vital signs
- Resting ECGs
- Columbia Suicide-Severity Rating Scale (C-SSRS)
- Clinical laboratory assessments including biochemistry, hematology, urinalysis, and special labs to monitor for vitamin deficiencies

- Concomitant medication usage
- Adverse event monitoring, including for the development of sleep attacks, melanoma, or excessive impulsive behavior
- Monitoring complications of the infusion device
- Tolerability assessed by number of subjects who complete the study

Maintenance of efficacy will be assessed by evaluating the mean change from baseline in the following:

- Off time, On time with troublesome dyskinesia and On time without troublesome dyskinesia as measured by the Parkinson's Disease Diary
- UPDRS total score, Parts I, II, III and IV scores, and dyskinesia item score
- PDQ-39 summary index and domain scores

For the analysis of change from baseline in efficacy measures, each subject's baseline will be their baseline measure in the first LCIG study in which they participated (e.g., Study S187.3.001, S187.3.002 or S187.3.004).

7.0 Study Design

7.1 Overall Study Design and Plan Description

This is a Phase 3B, open-label, multi-center study of the long-term safety and tolerability of LCIG in the continuation of treatment of approximately 275 advanced Parkinson's disease subjects with a good therapeutic response on LCIG with regard to the treatment of persistent severe motor fluctuations. The study will be conducted at approximately 70 centers. In addition, maintenance of efficacy will be evaluated at approximately 28 US sites.

Only subjects who have completed Study S187.3.003 or S187.3.004 will qualify for enrollment in this study. Following informed consent, subjects will have their inclusion/exclusion criteria assessed prior to beginning treatment in this study. Subjects are allowed to have a caregiver, if appropriate, assist them with study requirements,

i.e., care of the pump and tubing, etc. and the caregiver will have been trained accordingly.

The initial LCIG dose will be identical to the dose that the subject was receiving at the end of the previous open-label LCIG study. Subsequent dose adjustments will be made as clinically indicated by the Investigator.

In this open-label study, a recommendation will be made to Investigators to withhold concomitant PD treatments if deemed medically safe and clinically appropriate. The initiation of additional PD medication may be medically indicated and is allowed at the discretion of the Investigator. Also, the dosages of these other PD medications can be adjusted upward or downward as needed based on the status of the subject's condition or the development of adverse effects; resumption of discontinued PD medications may also be necessary.

In addition to the morning dose and the continuous infusion, subjects will be allowed to self-administer additional doses of LCIG to address immediate subjective needs, such as the deterioration of motor function. If subjects find it necessary to self-administer an increasing number of extra doses (> five/day) of LCIG, they will be instructed to contact the Investigator for appropriate follow-up care (adjustment of continuous infusion) as needed.

Subject visit days should ideally match the target clinic visit days; however, a 14-day visit window will be allowed as necessary. Attempt should be made to bring the subject back on the target visit day.

The final visit in the previous open-label LCIG study will provide baseline assessments for the S1878.3.005 study. Subjects will be reassessed every 6 months for the appropriateness of the continuation of treatment with LCIG. If the subject is deemed inappropriate for continued treatment by the Investigator, the subject would be discontinued from treatment and the PEG-J will be removed, with a follow-up visit

occurring 1 week later. For subjects who elect not to continue LCIG treatment, the PEG-J will be removed, and a follow-up clinic visit will occur 1 week later.

Safety assessments should include physical examination, neurological exam, orthostatic vital signs, weight, adverse event monitoring, assessment of impulsive behavior and sleep attacks, melanoma check, electrocardiogram (ECG), clinical hematology, biochemistry, special labs to monitor for vitamin deficiencies, and urinalysis.

The following efficacy assessments will be completed at US sites:

- Parkinson's Disease Diary[®] assessment of motor state completed for the 3 consecutive days prior to each clinic visit (excluding the drug dispensation visits),
- Unified Parkinson's Disease Rating Scale (UPDRS), and
- Parkinson's Disease Questionnaire-39 (PDQ-39).

At each visit, complications or adverse events with the infusion device (i.e., the tubing system and the pump) will also be recorded and reported. Tube placement will be checked by radiography if there is a clinical indication that the tube has been displaced. The tube will be repositioned, if needed, to the original placement site just beyond the ligament of Treitz. At each visit the tube insertion site, including the stoma, will also be inspected. On a yearly basis, at a minimum, an assessment will be made of the need for a replacement of the PEG-J. The frequency of replacement should be in accordance with local practice.

The protocol duration is planned until the finished product is available commercially in the respective countries where subjects are participating in the study. The expected protocol duration will continue through successful NDA and subsequent approval (approximately 4 years). ***The protocol duration will be extended 4 years in the UK from the approval date of Amendment 3.01. If it is deemed necessary to continue treatment after 4 years in the UK, either an amendment to the current protocol will be made or a new protocol will be submitted.***

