The efficacy of upper-intestinal administration of levodopa has been demonstrated in clinical investigations by decreasing motor fluctuations compared to standard oral therapy. Results of a 3-week open-label cross-over study (NPP-001-02), with blinded assessments of efficacy, demonstrated clinical and statistical superiority of LCIG compared to standard oral therapy with regard to motor fluctuations.^{2,15} Patients also reported significantly improved scores in two Quality of Life (QoL) instruments, the Parkinson's Disease Questionnaire (PDQ-39) and EuroQol Quality of Life Scale (EQ-5D).²

This open-label, multi-center, Phase 3B study will provide continued treatment with LCIG to subjects who have already participated in an open-label treatment study with the same treatment (S187.3.003 or S187.3.004). In countries where LCIG is not yet available

commercially, the treatment will be made available by the Sponsor in accordance with all local regulations as long as such is warranted by the therapeutic benefit. The latter will be determined in consultancy with the responsible neurologist, the subject and the Sponsor. Subjects who continue to receive study drug will be evaluated at least semi-annually by the Investigator. In cooperation with the investigational site, all necessary support will be provided by the Sponsor's local representatives. Additionally, the study will allow for observation of the long-term safety, tolerability, and maintenance of efficacy of LCIG administered for several years in a more naturalistic treatment environment.

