 - a. The final assessment in the previous open-label LCIG study will serve as the baseline assessment for this item.
 - b. Will be done as clinically indicated.
 - c. For women of childbearing potential.
 - d. Assessment performed once yearly.
 - e. Clinical supply visits should take place every 6 weeks \pm 7 days. These visits may take place at the hospital pharmacy and are for the purpose of dispensing clinical study drug and ancillary supplies. Other assessments may be completed during these visits if required. When scheduling the 6 weekly drug dispensing visits, the site should always refer back to the baseline visit. Every attempt should be made to pick up drug on the original targeted dates (\pm 7 days).
 - f. The "Already Enrolled Subjects" C-SSRS is to be the first assessment scale administered to the subject. At each subsequent assessment, the "Since Last Visit" C-SSRS scale should be administered. If the subject has previously completed the "Already Enrolled Subjects" scale in the S187.3.003 study, the subject should complete the "Since Last Visit" scale at all scheduled time points outlined in [Table 2](#) in this study. For subjects with a C-SSRS completed at their S187.3.003 final visit, that S187.3.003 final visit C-SSRS assessment will be considered baseline for the S187.3.005 study. For all other subjects, the first C-SSRS assessment completed in this study will serve as baseline.
 - g. The Daily Dosing Diary and the Parkinson's Disease Diary will be completed by subjects or their caregivers for the 3 consecutive days prior to each clinic visit at US sites only.
 - h. The UPDRS and the PDQ-39 will be completed at US sites only.

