13.3 Statistical Methods

Safety Analysis

The Safety Population will be used for the analysis of the safety and tolerability data.

Adverse events will be coded using the Medical Dictionary for Regulatory Activities (MedDRA). A treatment-emergent adverse event (TEAE) is defined as any adverse event that begins or worsens in severity on or after the first dose of study drug in the current study and within 30 days of the end of LCIG treatment in the current study. For subjects transferring to commercial product, the end of treatment in the current study will be the last dose of study drug. For subjects who are discontinuing LCIG treatment, the end of treatment in the current study will be the removal of the PEG-J tube. The following summaries of TEAE's will be prepared:

- Incidence of treatment-emergent adverse events
- Incidence of treatment-emergent serious adverse events

- Incidence of treatment-emergent adverse events resulting in study termination
- Incidence of treatment-emergent adverse events of special interest

The following additional analyses of safety will also be prepared:

- Summary of vital sign and weight values and mean change from Baseline over time
- Incidence of potentially clinically significant vital sign and weight values
- Summary of clinical lab values and mean change from Baseline to Endpoint
- Summary of special lab values and mean change from Baseline over time
- Incidence of potentially clinically significant clinical lab values
- Summary of MIDI at Baseline and during treatment
- Summary of C-SSRS
- Incidence of device complications

Efficacy Analysis

The Efficacy Population will be used for analyses of efficacy. The mean change from baseline to endpoint will be summarized for the following efficacy endpoints.

- "Off" time as measured by the Parkinson's Disease Diary
- "On" time without troublesome dyskinesia (sum of "On" time without dyskinesia and "On" time with non-troublesome dyskinesia) as measured by the Parkinson's Disease Diary
- UPDRS total score, Parts I, II, III and IV scores, and dyskinesia item score
- PDQ-39 summary index and domain scores

For the analysis of change from baseline in efficacy measures, each subject's baseline will be their baseline measure in the first LCIG study in which they participated (e.g., Study S187.3.001, S187.3.002 or S187.3.004).

Additional Analysis

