6.4.6 Treatment Period

Data collected on the Date of the First 3005 LCIG Infusion (Day 1) will be assigned to the Baseline Period. However, adverse events and concomitant medications starting on Day 1 will be assigned to the Treatment Period (worst case scenario).

A Gap Period (number of days) is defined to include data collected after the end of the relevant Treatment Period in the analysis. For this study, the Gap Period will be 30 days for adverse events and 1 day for all other assessments.

For efficacy assessments the Treatment Period is defined as the Period from the Date of the First 3005 LCIG Infusion up to and including the Date of the Last 3005 LCIG Infusion + Gap Period (1 day). For safety assessments the Treatment Period is defined as the Period from the Date of the First 3005 LCIG Infusion up to and including the Date of the Last 3005 PEG-J Exposure + Gap Period (30 days for adverse events and 1 day for all other assessments).

The Endpoint value for a variable is defined as the last non-missing value assigned to the Treatment Period for the subject.

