9.9 Efficacy Analyses

Subject Samples:	Tables	Efficacy Sample and US Subset
	Listings	All subject consented
	Figures	Not applicable
Subgroups:		First LCIG infusion study (3001/3002, 3003 or 3004), troublesome dyskinesia at initial LCIG infusion (< 1 hour, > 1 hour), dose of levodopa at initial LCIG infusion (< 1250 mg/day, > 1250 mg/day), and levodopa monotherapy during Study 3005 (yes, no)
Abbreviation:		QS

Standard Presentations

QST001 The average daily normalized "off" time will be summarized at initial LCIG infusion, at 3005 baseline and at 3005 endpoint as well as the change from initial LCIG infusion to 3005 endpoint and the change from 3005 baseline to 3005 endpoint. Descriptive statistics (including n, mean, minimum, maximum and 95% confidence interval) will be calculated.

Statistical tests for within group changes from initial LCIG infusion and from 3005 baseline will be implemented using PROC UNIVARIATE.

For the UNIVARIATE the following SAS[®] code will be used:

*PROC UNIVARIATE data = <SAS[®]-dataset> cibasic alpha = 0.05;
VAR OFFTIME;*

RUN;

The same methods defined above for average daily normalized "off" time will also be used to analyze the following assessments:

1. Change in average daily normalized "on" time without troublesome dyskinesia
2. Change in average daily normalized "on" time with troublesome dyskinesia
3. Change in average daily normalized "on" time with non-troublesome dyskinesia
4. Change in average daily normalized "on" time without dyskinesia
5. Change in the UPDRS total score, subscores of Parts I – IV and Part IV Questions 32, 33 and 34 (Dyskinesia items)
6. Change in the PDQ-39 summary index and each domain score

Variables derived from the PD Diary and PDQ-39 will be summarized for the Efficacy sample and the US subset of the Efficacy sample.

Variables derived from the UPDRS will be summarized for the US subset of the Efficacy sample.

QST002 The change from initial LCIG infusion to 3005 endpoint and from 3005 baseline to 3005 endpoint will be summarized by subgroup in the Efficacy sample – US Subset for the PD Diary variables.

QST003 The CGI score at 3005 endpoint will be summarized using the appropriate default summary statistics for the Efficacy sample.

Subject data listings will include:

- QSL001 A listing of Parkinson's Disease Diary data by-subject and within-subject by visit will be presented.
- QSL002 A listing of CGI-I scores by-subject and within-subject by visit will be presented.

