9.11.3 Vital Signs

Subject Samples:	Tables	Safety sample
	Listings	All subjects consented
	Figures	Not applicable
Subgroups:		Not applicable
Abbreviation:		VS

Standard Presentations

- VST001 Summary of quantitative vital signs assessments will be presented, for all centers/countries combined, using default summary statistics. At each assessed visit, summary statistics will be presented as well as for the change from Baseline at each post-baseline visit.
- VST002 For each variable with a PCS criterion (as presented in [Table 5](#)), the incidence of PCS values will be presented. The percentage per parameter is defined as the ratio of the number of subjects with at least one PCS value occurring at a post baseline visit that is more extreme than their baseline value and the total number of subjects in the subject sample with a post baseline measurement of the specified parameter.

In addition, all vital signs data will be presented as follows:

- VSL001 A listing of PCS values together with standard demographic data will be presented by-subject and within-subject by PCS vital signs test criterion by visit.
- VSL002 Vital signs data will be presented by-subject and within-subject by vital signs test and visit.

Study Specific Presentations

- VST003 For each variable with a PCS criterion (as presented in [Table 5](#)), the incidence of PCS values will be presented by visit. For a specific visit, the percentage per parameter is defined as the ratio of the number of subjects with at least one PCS value occurring at a specific post-baseline visit that is more extreme than their baseline value and the total number of subjects in the subject sample with a post baseline measurement of the specified parameter for the visit.

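### US efficacy is summarised only at each subject's last on-treatment value, and no table says when that value was taken, so maintenance cannot be tied to a duration of treatment

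*Protocol*

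**What the plan says.** The objective is about time. Protocol 6.2 sets out "to assess the maintenance of efficacy using data collected from US subjects", and Protocol 5.0 speaks of "maintenance of efficacy of LCIG administered for several years in a more naturalistic treatment environment". SAP 10.1 moves the efficacy baseline to the final value of the preceding open-label study so that the analysis concentrates on maintenance within Study 3005.

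The schedule is repeated. Protocol 7.1 describes the PD Diary as an "assessment of motor state completed for the 3 consecutive days prior to each clinic visit (excluding the drug dispensation visits". The footnote to Protocol Table 2 says that the diaries "will be completed by subjects or their caregivers for the 3 consecutive days prior to each clinic visit at US sites only". UPDRS and PDQ-39 are marked in the same two columns, the 6 Monthly Visit and Termination/Transfer.

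The analysis has a single follow-up point, in both documents. Protocol 13.3: "The mean change from baseline to endpoint will be summarized for the following efficacy endpoints". SAP 9.9 (QST001), for Off time: "time will be summarized at initial LCIG infusion, at 3005 baseline and at 3005 endpoint", with the same methods for the other diary variables, UPDRS and PDQ-39. SAP 6.4.6: "The Endpoint value for a variable is defined as the last non-missing value assigned to the Treatment Period for the subject". QST001 attaches a 95% confidence interval and a within-group test to the change.

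For vital signs, SAP 9.11.3 plans more: "At each assessed visit, summary statistics will be presented as well as for the change from Baseline at each post-baseline visit". SAP 9.11.2 plans the same for the vitamin-related tests.

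**The concern.** Whether benefit is held cannot be separated from how long it is held. Follow-up in this study is open-ended. Subjects stay until commercial product reaches them (SAP 8.1.5), so time on study depends partly on entry date. Those who leave early, including for lack of efficacy (Protocol 9.0), contribute an earlier last value on equal terms.

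A mean of last values therefore depends on the mix of follow-up times as well as on the course of the disease under treatment. Its confidence interval would be precise about a quantity with no stated time. A reader of the report could not tell a small change after short follow-up from a slow change after long follow-up. The visits that could separate the two are collected but not tabulated.

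**Working it through.** The plan gives no alpha, power, margin or effect size for efficacy (Protocol 13.4 and 13.5), so there is no planned figure to reproduce. The check is a trace, two counts and an illustration.

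**1. Where time could enter the efficacy output**

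- SAP 12.2, efficacy tables: 5 diary + 1 CGI-I + 9 PDQ-39 for the Efficacy sample; 5 diary + 6 UPDRS + 9 PDQ-39 + 20 diary-by-subgroup for the US Subset. Total 15 + 40 = 55. None is by visit or by treatment year.
- SAP 6.4.9 lists what is summarised by 3005 Treatment Year. Efficacy is not on the list.
- SAP 8.1.2: no efficacy subgroup is based on duration of treatment.
- EXT001 (SAP 9.8) gives exposure for the Safety sample and its US Subset. It is not run on the Efficacy sample and does not give the day of the efficacy endpoint.
- Intermediate efficacy visits appear in the by-visit listings (QSL001, QSL003, QSL004). They can also enter through diary rule 8 in SAP 8.4.1, which averages in the previous visit when only one valid diary day exists.

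**2. Spread of endpoint times the SAP allows**

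SAP Table 2 runs from Month 6 (from Day 2) to Month 84 (after Day 2430). 2430 / 365.25 = 6.7 years. No minimum or target time is set for the endpoint.

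**3. Visits left out of the summaries**

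- Protocol date with the US efficacy assessments: 17 December 2013. Interim cutoff: 30 September 2015 (SAP 4.0).
- Days between: 14 + 365 + 273 = 652. 652 / 180 = 3.6, so 3 to 4 six-monthly visits for a US subject who continued throughout.
- One of them supplies the endpoint, leaving 2 to 3 outside every table.
- This is an upper range. Sites need ethics approval before adopting a substantial amendment (Protocol 15.1), and subjects leave when commercial product becomes available. The final report has no cutoff (SAP 6.4.1).

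**4. What the pooled mean measures (assumed slopes; none is in the documents)**

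If Off time worsens linearly by s h/year and the timing of the endpoint is unrelated to the slope, mean change at endpoint = s × mean endpoint time.

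- s = 0.3 h/year at mean times of 1, 2, 4 and 6 years: 0.3, 0.6, 1.2 and 1.8 h.
- Half the endpoints at 0.5 years and half at 4 years gives a mean time of (0.5 + 4) / 2 = 2.25 years:

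| s (h/year) | Change at 0.5 y | Change at 4 y | Pooled mean |
|---|---|---|---|
| 0.1 | 0.05 | 0.4 | 0.23 |
| 0.25 | 0.12 | 1.0 | 0.56 |
| 0.5 | 0.25 | 2.0 | 1.13 |

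The middle pooled value, 0.56 h, would also arise from s = 0.5 h/year with a mean time of 0.5625 / 0.5 = 1.125 years. A twofold difference in rate gives the same reported number, and no planned table tells the two apart.

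**5. What a table by time could and could not show**

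SAP 8.4 says that efficacy measures were dropped at Amendment 1 and restored, for US sites, at Amendment 4. A subject already on treatment at the first interim cutoff (4 May 2012) had at least 592 days on study by 17 December 2013 (365 + 227). That subject can have no Amendment 4 value in Year 1. Early bands will therefore be thin, and different bands will hold different subjects.

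**The case against.** The strongest reply is that the SAP does what the protocol asks. Protocol 13.3 itself specifies change from baseline to endpoint. That stands. A reader might infer that the SAP departs from the protocol, but the two agree. The gap lies between the schedule and objective on one side and the analysis on the other, in both documents.

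A reader might also infer that the intermediate data are discarded. They are not: they are listed by subject and visit, and diary rule 8 can use them. What is missing is any summary. EXT001 is a partial answer, since for subjects who complete the termination visit the endpoint falls near the end of exposure. But it covers a different sample and does not give the endpoint day.

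A further inference would be that the plan loses much precision. In simulations under assumed inputs (60 or 100 US subjects, 1 to 4 visits, residual SD 1.5 to 2 h, slope SD 0.3 to 0.6 h/year), a yearly slope from last values alone had 2 to 17% more variance than one from all visits. That is an interval 1 to 8% wider (√1.02 and √1.17). Both are slope estimators, however, and SAP 9.9 estimates no slope. Precision is not the reason for the change.

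Nor do the documents show that a mixed model is needed. It would draw a line across the period with no scheduled efficacy assessments, with few values per subject, and its longest follow-up would come only from those who stayed.

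The contrast with vital signs is limited too. Those were scheduled under every amendment shown in SAP 12.1, so it shows only that the windows and table format already exist.

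Finally, efficacy is secondary. The primary objective is access and the primary statistical objective is safety. No error rate or decision rule changes.

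**Conclusion.** The point holds as a gap in description. As planned, the US efficacy result is one mean change over endpoint times that may range from Day 2 to beyond Day 2430. Its timing is unreported, and the other visits appear only in listings apart from diary rule 8. It cannot be tied to any duration of treatment, which is what a maintenance objective over several years needs.

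The size cannot be given from the documents, because they contain no rate of change and no distribution of endpoint times. The figures above rest on assumed linear slopes and show only that the reported change scales with mean follow-up. By the 2015 interim at most 2 to 3 visits per continuing US subject would be outside the tables. The final report may have more.

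A reader might go further and conclude that the planned endpoint mean is wrong or biased in a known direction. Nothing in the documents supports that. It is a valid description of last values. This is a cheap improvement, not a fault that undermines the study.

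**What to change.** In SAP 9.9, for the Efficacy sample US Subset:

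- Add a descriptive table for each PD Diary, UPDRS and PDQ-39 variable, giving the value and the change from 3005 baseline (n, mean, SD, 95% CI) by time since 3005 Day 1. Use either the visit windows of SAP Table 2, which already have a rule for choosing one assessment per window, or the Treatment Year bands of SAP Table 3. With year bands, add a rule that each subject counts once per band.
- In each QST001 US table, print the median and range of endpoint study day.
- Keep the planned endpoint tables.
- State in the text or footnotes that bands contain different subjects, that early bands may be sparse because Amendment 4 reached subjects at different study days, and that subjects who left before Amendment 4 are not represented among its assessments.

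A mixed model for yearly change may be added, labelled optional and exploratory, with its assumptions about linearity and dropout stated.

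The cost is SAP wording, one added line in 20 existing US tables (5 diary + 6 UPDRS + 9 PDQ-39) and one matching set of new tables, some with small n. All data and date variables are already collected. Protocol 13.3 need not change if the new tables are recorded in SAP 10.1 as additions.
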